8. Active and measurable disease, defined by serum paraprotein (M-protein) ≥ 0.5 g/dL, 24-hour urine Bence Jones protein of ≥ 200 mg, or abnormal serum free light chain ratio with involved light chain of ≥ 10 mg/dL (100 mg/L).
9. Have adequate organ function as defined in the following table (Table 3.3.1). Specimens must be collected within 10 days prior to the start of study treatment.

Table 3.3.1 Adequate Organ Function Laboratory Values

System	Laboratory Value
Hematological	
Absolute neutrophil count (ANC)	$\geq 500/\mu\text{L}$ ^{a, b}
Platelets	$\geq 25\,000/\mu\text{L}$ ^{a, b}
Hemoglobin	$\geq 8.0\text{ g/dL}$ ^{a, b}
Renal	
Creatinine OR Measured or calculated ^c creatinine clearance (GFR can also be used in place of creatinine or CrCl)	$\leq 1.5 \times \text{ULN}$ OR $\geq 30\text{ mL/min}$ for participant with creatinine levels $>1.5 \times$ institutional ULN
Hepatic	
Total bilirubin	$\leq 1.5 \times \text{ULN}$ OR direct bilirubin $\leq \text{ULN}$ for participants with total bilirubin levels $>1.5 \times \text{ULN}$

AST (SGOT) and ALT (SGPT)	$\leq 2.5 \times \text{ULN}$ ($\leq 5 \times \text{ULN}$ for participants with liver metastases)
ALT (SGPT)=alanine aminotransferase (serum glutamic pyruvic transaminase); AST (SGOT)=aspartate aminotransferase (serum glutamic oxaloacetic transaminase); GFR=glomerular filtration rate; ULN=upper limit of normal.	
a Growth factor and/or transfusion support is permissible to stabilize participant prior to study treatment if needed.	
b No lower limit if cytopenia is related to bone marrow involvement.	

^c Creatinine clearance (CrCl) should be calculated per institutional standard.

Note: This table includes eligibility-defining laboratory value requirements for treatment; laboratory value requirements should be adapted according to local regulations and guidelines for the administration of specific chemotherapies.

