7.1.1 Methods for Evaluation of Measurable Disease

For participants with measurable disease by M-protein (serum M-protein ≥ 1 g/dL), response criteria will be determined primarily by SPEP/SPIE. For participants with measurable disease by 24-hour UPEP/UPIE (≥ 200 mg/24 hours) but not by SPEP/SPIE (M-protein < 1 g/dL), response criteria will be determined primarily by UPEP/UPIE. For participants with only measurable disease by FLC and without measurable disease by SPEP/SPIE and UPEP/UPIE, response criteria will be determined primarily by FLC levels.

Participants will also undergo 24-UPEP/UPIE at certain time points depending on 24-hour UPEP/UPIE at screening.

- Participants who have measurable disease by SPEP/SPIE (M-protein ≥ 1 g/dL) and by 24-hour UPEP/UPIE (≥ 200 mg/24 hours) at screening will undergo a 24-hour UPEP/UPIE at time of suspected sCR, CR, VGPR, PR, and progressive disease.
- Participants with measurable disease by SPEP/SPIE (M-protein ≥ 1 g/dL) but no measurable 24-hour UPEP/UPIE (< 200 mg/24 hours) at screening will undergo a 24-hour UPEP/UPIE at time of suspected sCR, CR, VGPR, and progressive disease to confirm IMWG response criteria.
- Participants with only measurable disease by FLC and without measurable disease by SPEP/SPIE and UPEP/UPIE at screening will undergo 24-hour UPEP/UPIE at time of suspected sCR, CR, VGPR, and progressive disease.

For participants who develop serologic markers consistent with a complete response (disappearance of serum and urine M-protein on electrophoresis for patients with measurable M-protein at treatment initiation or normalization of the free light chain ratio for those with

elevated free light chain markers but unmeasurable M-protein at treatment initiation), a bone marrow biopsy is required to confirm IMWG complete response.

For participants with known soft tissue plasmacytomas or extramedullary disease on enrollment, imaging (PET/CT, CT, or MRI) is recommended to confirm IMWG response for patients who achieve at least a hematologic partial response. Imaging is also recommended if there is clinical concern for progressive disease.

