7.1.2 Response Criteria

The primary endpoint is the overall response rate (ORR), defined as the proportion of patients achieving a partial response (PR) or better (including sCR, CR, and VGPR) after 4 cycles of pembrolizumab therapy. The response criteria are described below (see Appendix 6 for additional details) :

- Stringent complete response (sCR)
 - Requires achieving complete response (CR) defined below plus normal FLC ratio and absence of clonal plasma cells by immunohistochemistry or flow cytometry
- Complete response (CR)
 - *For patients with measurable serum or urine M-protein on enrollment:* negative immunofixation of serum and urine and < 5% plasma cells in the bone marrow is required
 - *For patients without measurable serum and urine M-protein levels on enrollment:* a normal FLC ratio (0.6 – 1.65) is necessary in addition to the above criteria
 - *For patients with known soft tissue plasmacytomas or extramedullary disease on enrollment,* disappearance of all soft tissue plasmacytomas is required to meet CR
- Very good partial response (VGPR)
 - *For patients with measurable serum or urine M-protein on enrollment:* detectable M-protein on immunofixation but not on electrophoresis or ≥ 90% reduction in serum M-protein plus urine M-component < 100 mg/24 hours is required.
 - *For patients without measurable serum and urine M-protein levels on enrollment (only measurable disease is by serum FLC):* ≥ 90% decrease in the difference between involved and uninvolved free light chains is required.
- Partial response (PR)
 - *For patients with measurable serum and urine M-protein on enrollment:* ≥ 50% reduction of serum M-protein and reduction in 24-hour urinary M-protein by ≥ 90% to < 200 mg/24 hours are required.
 - *For patients with measurable serum but without measurable urine M-protein on enrollment:* ≥ 50% reduction of serum M-protein is required.
 - *For patients without measurable serum and urine M-protein levels on enrollment (only measurable disease is by serum FLC):* ≥ 50% decrease in the difference between involved and uninvolved free light chains is required (provided the

serum-free light chain assay shows involved level > 10 mg/dL and the serum-free light chain is abnormal).

- *For patients with known soft tissue plasmacytomas or extramedullary disease on enrollment, $\geq 50\%$ reduction in size of soft tissue plasmacytomas is required in addition to the above criteria.*
- Stable Disease (SD)

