Appendix 6 IMWG Uniform Response Criteria

Response	IMWG criteria ⁴⁶
Stringent complete response (sCR)	CR as defined below plus normal FLC ratio and absence of clonal plasma cells by immunohistochemistry or flow cytometry
Complete response (CR)	Negative immunofixation of serum and urine and disappearance of any soft tissue plasmacytomas and < 5% plasma cells in bone marrow. For patients without measurable serum and urine M-protein levels at baseline: a normal FLC ratio (0.6 – 1.65) is necessary in addition to the above criteria
Very good partial response (VGPR)	Serum and urine M-component detectable by immunofixation but not on electrophoresis or ≥90% reduction in serum M-component plus urine M-component < 100 mg/24 hours For patients without measurable serum and urine M-protein levels at baseline: ≥90% decrease in the difference between involved and uninvolved free light chains
Partial response (PR)	≥ 50% reduction of serum M-protein and reduction in 24-hour urinary M-protein by ≥ 90% to < 200 mg/24 hours. If serum and urine M-protein are not measurable, a decrease ≥50% in the difference between involved and uninvolved FLC levels is required in place of the M-protein criteria. If serum and urine M-protein are not measurable, and serum-free light assay is also not measurable, ≥ 50% reduction in bone marrow plasma cells is required in place of M-protein, provided baseline percentage ≥ 30%. In addition to the above criteria, if present at baseline, ≥50% reduction in the size of soft tissue plasmacytomas is also required.
Stable Disease (SD)	Not meeting criteria for CR, VGPR, PR, or PD

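### As written, the urine limit for PR is stricter than the one for VGPR when baseline urine M-protein is 200 to just under 1000 mg/24 h, and urine-only participants have no written PR line, so some responses can be scored as stable disease in the primary endpoint

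*Combined protocol and SAP*

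**What the plan says.** The primary endpoint is the proportion with PR or better after 4 cycles, and VGPR, CR and sCR all count. Stable disease is the residual category in section 7.1.2.

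- **PR, serum and urine both measurable (7.1.2):** a serum fall of at least 50% and a "reduction in 24-hour urinary M-protein by ≥ 90% to < 200 mg/24 hours are required". Appendix 6 uses the same urine wording: "reduction in 24-hour urinary M-protein by ≥ 90% to < 200 mg/24 hours".
- **VGPR, serum or urine measurable (7.1.2):** there are two routes. One is "detectable M-protein on immunofixation but not on electrophoresis"; the other is "≥ 90% reduction in serum M-protein plus urine M-component < 100 mg/24 hours is required". Neither sets a percentage for urine.
- **PR lines in 7.1.2:** these cover serum plus urine, serum without urine, and FLC-only disease. No line covers urine without serum.
- **Urine-only participants:** inclusion criterion 8 (3.3.1) accepts "24-hour urine Bence Jones protein of ≥ 200 mg" as sufficient measurable disease. Section 7.1.1 says that where urine is measurable but serum is not, "response criteria will be determined primarily by UPEP/UPIE", and gives no threshold. Appendix 6 replaces the M-protein conditions only when serum and urine are both unmeasurable.

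Section 9.1.1 sets the decision rules: stop after stage 1 with 0 or 1 response in 15, and reject the 10% null with 6 or more in 25. It states 80% power at a 30% response rate, a one-sided 5% type I error, and a 55% chance of early stopping under the null.

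**The concern.** Response categories should be nested, so that anyone who meets the deeper category also meets the shallower one. Here they are not. Over a range of baselines, a urine value good enough for VGPR is not good enough for PR. A participant whose serum fall is adequate for PR but short of VGPR can therefore miss both categories and drop to SD.

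Urine-only participants have a separate gap. They are eligible and have a designated marker, but the PR definition in 7.1.2 does not mention them, and the default line in Appendix 6 still asks for a serum fall of at least 50%.

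Both defects sit in the PR boundary, which is what the primary endpoint counts. With 25 participants, each call moves ORR by 1/25 = 4 percentage points, and one call can decide either the stage 1 rule or the final rule. In an open single-arm trial, an unsettled definition also leaves room to choose a reading after the laboratory values are known.

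**Working it through.** **1. The plan's own figures.** Inputs from 9.1.1: n1 = 15, stop at 1 or fewer; n = 25, reject at 6 or more; response rates 10% and 30%.

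P(reject | p) = Σ over x = 2 to 15 of P(X1 = x) × P(X2 ≥ 6 − x), with X1 ~ Bin(15, p) and X2 ~ Bin(10, p). P(stop | p) = P(X1 ≤ 1).

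- p = 0.10: P(stop) = 0.549, P(reject) = 0.033.
- p = 0.30: P(stop) = 0.035, P(reject) = 0.802.

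These agree with the stated 55%, 5% limit and 80%. The design is sound; the problem is in the definition that feeds it.

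**2. Urine limits.** Read literally, PR needs a fall of at least 90% that also ends below 200 mg/24 h. With baseline U, the final value must be at most 0.1 × U and also below 200. VGPR needs a value below 100.

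| Baseline U (mg/24 h) | PR limit | VGPR limit | Tighter on urine |
|---|---|---|---|
| 200 | ≤ 20 | < 100 | PR |
| 400 | ≤ 40 | < 100 | PR |
| 800 | ≤ 80 | < 100 | PR |
| 999 | ≤ 99.9 | < 100 | PR |
| 1000 | ≤ 100 | < 100 | effectively equal |
| 1500 | ≤ 150 | < 100 | VGPR, as expected |
| 2000 and above | < 200 | < 100 | VGPR, as expected |

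The order is inverted when 0.1 × U < 100, that is, for U from 200 to just under 1000. The absolute limit of 200 does nothing when 0.1 × U < 200, that is, for any U below 2000.

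**3. What happens to a participant (both markers measurable, U = 400).**

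- Serum −60%, urine 400 to 80. The urine fall is 320/400 = 80%, so PR fails. Urine is below 100, but serum misses the 90% needed for VGPR, and protein still visible on electrophoresis closes the other VGPR route. Without progression, the result is SD and a non-response.
- Serum −92%, urine 400 to 80. PR fails in the same way, but VGPR is met. This participant counts in ORR.

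The loss is therefore limited to participants with serum down at least 50% but short of VGPR, and urine below 100 mg/24 h but down by less than 90%.

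**4. Urine-only participants.** Section 7.1.2 gives no PR line. Appendix 6 waives the serum part only if urine is also unmeasurable, so its default still applies. The group includes more than those with no serum protein: inclusion criterion 8 accepts serum from 0.5 g/dL, while 7.1.1 treats serum below 1 g/dL as not measurable. A participant with serum 0.8 g/dL and urine of at least 200 mg/24 h is scored by urine.

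**5. Size, under an assumption.** Let s be the share of true responders scored SD. The documents do not give s. The observed rate is then 0.30 × (1 − s).

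| s (assumed) | Observed rate | Power | Stage 1 stop |
|---|---|---|---|
| 0 | 30% | 80.2% | 3.5% |
| 5% | 28.5% | 75.4% | 4.6% |
| 10% | 27% | 69.9% | 5.8% |
| 20% | 24% | 57.1% | 9.4% |

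The literal rule can only remove responses, so it cannot raise the type I error.

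**The case against.** Four things can fairly be said against this point.

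*It affects few participants.* Anyone who reaches VGPR still counts, so with both markers measurable the loss needs the conjunction in step 3. That stands. The number could be zero among 25, and the power figures illustrate a range rather than estimate it.

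*Urine-only participants are not without guidance.* Section 7.1.1 names urine as their main marker, and the VGPR and CR lines cover measurable serum or urine. A reader might infer that these participants have no workable PR rule. That goes too far, because the urine half of the PR line could be applied to them. But that reading is not written down, it conflicts with the default line in Appendix 6, and it keeps the inversion.

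*Nobody has shown that true responses are lost.* A reader might infer that every such urine fall is a real response that the plan discards. The documents do not establish that. They show that the plan's own categories are out of order, so at least one boundary is not what was meant. Which wording was meant must be checked against the IMWG criteria that the protocol cites.

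*The obvious correction has its own risk.* If the percentage and the absolute limit become alternatives, a urine-only participant going from 205 to 195 mg/24 h, a fall of 10/205 = 5%, would meet PR. To illustrate with assumed shares: if 5% of participants were of this kind and half of their non-responses became PR under a 10% null, the rate would be 0.10 + 0.05 × 0.90 × 0.5 = 12.25%, and P(reject) would rise from 3.3% to 7.6%. This objection stands and shapes the fix.

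**Conclusion.** The defect is real. Section 7.1.2 and Appendix 6 share the same wording, so neither corrects the other. For baseline urine of 200 to just under 1000 mg/24 h, PR is harder to meet on urine than VGPR, and an identifiable group of participants falls to SD as a result. The missing urine-only PR line is a second defect in the same definition.

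The direction is known: fewer counted responses, lower ORR and power, and more futility stops, with no inflation of type I error. The size is not known. A power of 69.9% and a stage 1 stop of 5.8% at a true ORR of 30% hold only if 10% of true responders are lost. A reader might conclude that the trial's power is in fact below 80%; the documents do not support that, because they give neither the share with measurable urine nor the distribution of baseline values. The inversion itself needs no assumption beyond the literal reading of the two criteria.

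**What to change.** Reconcile 7.1.1, 7.1.2 and Appendix 6 before responses are adjudicated:

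1. Reword the PR urine criterion so that any value meeting the VGPR urine limit also meets the PR one. Making the two limits alternatives (a fall of at least 90%, or to below 200 mg/24 h) does this, since a value below 100 is also below 200. First check the wording against the IMWG criteria cited in Appendix 6.
2. Add a PR line to 7.1.2 for participants with measurable urine but not serum M-protein, based on the urine criterion.
3. State in Appendix 6 that the serum and urine parts each apply only where that component was measurable at baseline.
4. Guard against trivial falls near 200 mg/24 h: keep the requirement in Appendix 6 for two consecutive assessments, and report ORR with and without urine-only participants whose baseline was just above the threshold. Set that margin before the data are reviewed.

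The cost is an amendment to three places in the text, one added sensitivity analysis, and re-scoring of anyone already assessed under version 1.8 or before. It needs no new tests, visits or participants.

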7.1.3 Time to Event Definitions

Progression-free survival (PFS) is defined as the duration of time from start of treatment to time of progression or death, whichever occurs first.

Overall survival (PFS) is defined as the duration of time from start of treatment to time of death.

Time-to-next treatment (TNT) is defined as the duration of time from start of treatment to start of next line therapy.

7.2 Evaluation of Safety

The safety parameters for this study include all laboratory tests and hematological abnormalities, physical findings, and spontaneous reports of adverse events reported to the investigator by participants.

Toxicity will be assessed according to the ASTCT criteria for CRS and ICANS and NCI CTCAE version 5.0 for all other toxicities.

Safety analyses will be performed for all participants who receive at least one dose of pembrolizumab.

8 Safety Parameters

8.1 Definitions

8.1.1 Adverse Event (AE)

Adverse event means any untoward medical occurrence associated with the use of an intervention in humans, whether or not considered intervention-related (21 CFR 312.32 (a)).

8.1.2 Serious Adverse Event (SAE)

An adverse event is considered *serious* if, in the view of either the investigator or sponsor, it results in any of the following outcomes:

- Death
- Life-threatening adverse event
 - An adverse event is considered life-threatening if, in the view of either the investigator or sponsor, its occurrence places the participant at immediate risk of death. It does not include an adverse event that, had it occurred in a more severe form, might have caused death.
- Inpatient hospitalization or prolongation of existing hospitalization
- A persistent or significant incapacity or substantial disruption of the ability to conduct normal life function
- Congenital anomaly/birth defect

Important medical events that may not result in death, are life-threatening or require hospitalization may be considered serious when, based upon appropriate medical judgment, they may jeopardize the participant and may require medical or surgical intervention to prevent one of the outcomes listed in this definition. Examples of such medical events include allergic bronchospasm requiring intensive treatment in an emergency room or at home, blood dyscrasias or convulsions that do not result in inpatient hospitalization, or the development of drug dependency or drug abuse.

8.1.3 Unanticipated Problem (UP)

An unanticipated problem (UP) is any incident, experience, or outcome that meets all of the following criteria:

- 1) unexpected (in terms of nature, severity, or frequency) given (a) the research procedures are described in the protocol-related documents, such as the IRB-approved research protocol and informed consent document; and (b) the characteristics of the subject population being study;
- 2) related or possibly related to participation in the research; and
- 3) suggests that the research places subjects or others at a greater risk of harm (including physical, psychological, economic, or social harm) related to the research than was previously known or recognized.

Only a small subset of adverse events occurring in human subjects participating in research will meet these three criteria for an unanticipated problem. Furthermore, there are other types of incidents, experiences, and outcomes that occur during the conduct of human subjects research that represent unanticipated problems but are not considered adverse events. For example,

some unanticipated problems involve social or economic harm instead of the physical or psychological harm associated with adverse events. In other cases, unanticipated problems place subjects or others at increased risk of harm, but no harm occurs.

8.2 Classification of Adverse Events

8.2.1 Severity

Adverse events are graded according to the National Cancer Institute Common Terminology Criteria for Adverse Events (CTCAE) version 5.0.

8.2.2 Attribution

Adverse events are given an assignment of attribution or relationship to the investigational agent(s) or study procedure. Attribution categories are:

- Definite – The adverse event is clearly related to the investigational agent(s) or study procedure.
- Probable – The adverse event is likely related to the investigational agent(s) or study procedure.
- Possible – The adverse event may be related to the investigational agent(s) or study procedure.
- Unrelated – the adverse event is clearly not related to the investigational agent(s) or study procedure.

8.2.3 Expectedness

An adverse event is considered unexpected if the nature, severity, or frequency of the event is not listed in the study protocol, product inserts, investigator brochure, or informed consent document.

8.3 Recording of Adverse Events

Refer to the Data Safety Monitoring Plan, located in Appendix 2.

8.4 Expedited Reporting

8.4.1 Reporting to the HDFCCC Data and Safety Monitoring Committee

If a death occurs during the treatment phase of the study or within 30 days after the last administration of the study drug(s) and it is determined to be related either to the study drug(s) or to a study procedure, the UCSF PI or his/her designee must notify the DSMC Chair (or qualified alternate) within 1 business day of knowledge of the event. The contact may be by phone or e-mail.

8.4.2 Reporting to Institutional Review Board

The UCSF PI must report events to the IRB according to institutional guidelines.

8.4.3 Expedited Reporting to the FDA

If the study is being conducted under an IND, the Sponsor (or the Sponsor-Investigator) is responsible for determining whether or not the suspected adverse reaction meets the criteria for expedited reporting in accordance with federal regulations (21 CFR §312.32).

The Sponsor (or Sponsor-Investigator) must report in an IND safety report any suspected adverse reaction that is both serious and unexpected. The Sponsor needs to ensure that the event meets all three definitions:

- Suspected adverse reaction
- Unexpected
- Serious

If the adverse event does not meet all three of the definitions, it should not be submitted as an expedited IND safety report.

The timeline for submitting an IND safety report to FDA is no later than **15 calendar days** after the Investigator determines that the suspected adverse reaction qualifies for reporting (21 CFR 312.32(c)(1)).

Any unexpected fatal or life-threatening suspected adverse reaction will be reported to FDA no later than **7 calendar days** after the Investigator's initial receipt of the information (21 CFR 312.32(c)(2)).

Any relevant additional information that pertains to a previously submitted IND safety report will be submitted to FDA as a Follow-up IND Safety Report without delay, as soon as the information is available (21 CFR 312.32(d)(2)).

